7.8.2 Clinical Laboratory Tests

Stage 1 and up to end of fixed dosing period in Stage 2

In this study, clinical laboratory tests were done at local laboratories. Therefore, the reference ranges may not be the same. All laboratory test results will be summarized by period (run-in period, dose period, and washout period) using frequency distribution for low/normal/high or normal/abnormal. The denominators for calculating the percentages will be based on the number of subjects with non-missing values in the Safety Population.

Shift from baseline in laboratory parameters will be summarized by period for the Safety Population by period based on Low/Normal/High classification. The denominators for calculating the percentages will be based on the number of subjects with non-missing values at both baseline and each post-baseline analysis visit in the Safety Population.

Randomization period in Stage 2

Additionally, the above summaries will be provided for viral signs during the randomization period by treatment for randomized population.

All clinical laboratory assessments will be listed.

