4.4 Exclusion Criteria

- Unable or unwilling to provide informed consent or to comply with study procedures.
- Diagnosis of secondary constipation beyond that of PD
- Structural or metabolic diseases that affect the GI system
- Functional GI disorder
- Unable to withdraw the following medications 2 weeks prior to the dose-escalation period and throughout the study: Laxatives, opiates, sedatives, hypnotics, protein pump inhibitors or any medications which may cause constipation
- History of recent major surgery (within 60 days of screening)
- Any clinically significant abnormalities on screening laboratories or physical examination requiring further evaluation or treatment.
- Neurological disorder other than PD
- On treatment with intra-jejunal dopamine or carbidopa/levodopa (i.e. Duopa)
- Treatment with COMT inhibitors (entacapone, tolcapone, Stalevo)
- Patients starting a new PD medication or modifying an existing medication within 4 weeks prior to enrollment
- Unable to maintain a stable diet regimen
- Patients with a cognitive impairment that preclude them from understanding the informed consent
- Patients placed under legal guardianship
- Acute GI illness within 2 weeks of the baseline period
- History of major GI surgery (e.g. previous abdominal surgery, including Cholecystectomy), except that patients with uncomplicated appendectomy are allowed.
- ALT or AST > 1.5 X upper limit of normal (ULN) during screening

• Females who are pregnant or breastfeeding

• History of excessive alcohol use or substance abuse

Patient or caregiver unable to administer daily oral dosing.

• Participation in an investigational clinical study within the 6 months prior to dosing in

the present study.

• Any other reason, which in the opinion of the Investigator would confound proper

interpretation of the study.

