9.11 Laboratory Abnormalities

Clinical labs will be performed by a local laboratory. Labs to be drawn during the study include: serum chemistries, a hematology panel and urinalysis. A serum pregnancy test must be performed and the result must be negative prior to the entry of women of child bearing potential. The investigator must obtain verification that the local laboratory meets the standards for quality and consistency set by the College of American Pathologists.

Clinical laboratory reports must be reviewed by a physician for out-of-range values within 24 hours of receipt. Out-of-range values will be evaluated using the following notations:

- NS Not clinically significant
- LE Laboratory Error
- PT Patient abnormal; relates to the patient's usual state of health
- SG Significant, other. This value cannot be explained by any of the other flags.

By definition a lab value flagged as "SG" must be entered on the adverse clinical laboratory event page in the case report form. A laboratory test flagged "SG" must be repeated as soon as possible. The investigator may use his/her own judgment as to whether the abnormal finding is sufficient reason to immediately withdraw the patient from the study.

If a laboratory value is considered to be serious and life-threatening the patient should be immediately discontinued from the study and appropriate therapy started. Refer to sections **9.7-9.12** for definition of a serious adverse event and related terms, and to sections **9.13-9.16** for details on reporting a serious adverse event.

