4.3 Tolerability Evaluations

Tolerability will be measured by the following DLT endpoints: Dose Limiting Toxicity (DLT) will be the dose which induces repeated vomiting, diarrhea, abdominal pain or symptomatic postural hypotension within 24 hours of dosing. It is defined using the Common Terminology Criteria for Adverse Events (CTCAE) as:

- Recurrent vomiting: 3-5 episodes of vomiting within 24 hours of taking ENT-01 (i.e., 3-5 episodes of Grade 2 vomiting)

- Recurrent diarrhea: 4-6 episodes of diarrhea within 24 hours of taking ENT-01 (will be recoded as a Grade 2 diarrhea)
- Moderate Abdominal pain that limits instrumental activities of daily living within 24 hours of taking ENT-01 (Grade 2 AE)
- postural hypotension including Moderate dizziness, lightheadedness or fainting upon rising from lying to sitting or standing and severe enough to require medical intervention within 24 hours of taking ENT-01 (Grade 2 AE) or either a systolic blood pressure less than 80mmHg or diastolic blood pressure less than 40mm Hg

In addition, the following will also be considered dose limiting toxicity for the purpose of analyses:

- Elevation of LFTs > 3 times the upper limit of normal (ULN)
- A reduction of body weight of 10% or more

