8 DEFINITIONS AND CONVENTIONS FOR DATA HANDLING

8.1 Definition of Baseline

For all evaluations unless otherwise noted, baseline is defined as the most recent measurement prior to the first administration of study drug in Stage 1. Baseline can be the same date as first dose, given the measurement is expected prior to first dose when only date information is available.

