8.5 Handling of Repeated Clinical Laboratory Tests

For laboratories results at unscheduled visits, it will be treated as repeated laboratory results for the closest previous visit. The last repeat of laboratory results will be used in the summary tables for that visit. All the laboratory test results (original test results and repeated results) will be included in the data listings.

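### No laboratory table can show how large an ALT, AST or bilirubin rise was between 1 and 3 times ULN

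*SAP*

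**What the plan says.** SAP 7.8.2 notes that the tests are run at local laboratories whose reference ranges may differ. It then specifies two summaries. The first is counts: "All laboratory test results will be summarized by period (run-in period, dose period, and washout period) using frequency distribution for low/normal/high or normal/abnormal". The second is shifts: "Shift from baseline in laboratory parameters will be summarized by period for the Safety Population by period based on Low/Normal/High classification". All laboratory values are also listed.

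SAP 8.5 treats an unscheduled result as a repeat for the closest previous visit and adds: "The last repeat of laboratory results will be used in the summary tables for that visit". The same section keeps everything in the listings: "All the laboratory test results (original test results and repeated results) will be included in the data listings".

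Four other rules bear on the point:

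- Protocol 4.4 excludes "ALT or AST > 1.5 X upper limit of normal (ULN) during screening", so enzyme values above 1 and up to 1.5xULN may enter.
- SAP 4.3 counts a liver-test elevation as a DLT only above 3xULN. Protocol 3.1 (Period 2.1, individual stopping criteria) uses the same limit for AST, ALT and total bilirubin.
- Protocol 9.11 requires a value flagged as significant (SG) to be repeated. It also says that such a value "must be entered on the adverse clinical laboratory event page in the case report form".
- SAP 8.1 says that, unless otherwise noted, "baseline is defined as the most recent measurement prior to the first administration of study drug in Stage 1".

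**The concern.** Safety is a primary objective in both stages (SAP 3.1.1 and 3.2.1). Protocol 1.3 describes the trial as the first oral dosing of ENT-01 in man and names reversible hepatic enzyme elevation as the main dose-limiting toxicity of intravenous squalamine. A reader of the study report will want to know whether liver tests moved with dose, and by how much, below the stopping limit.

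The planned tables cannot answer that. High is one class from just above 1xULN upward, and the next threshold in any planned output is the DLT at more than 3xULN. A trivial excursion and a near-limit one look the same.

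The reason given in SAP 7.8.2, differing local ranges, is a good reason not to pool raw values. It is not a reason to drop size, because a result divided by its own laboratory's ULN is comparable across sites. The plan's entry, stopping and DLT rules already use that scale.

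**Working it through.** The plan gives no figure to reproduce. The check maps values, in multiples of ULN, to the planned outputs.

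**Inputs.** High means above 1xULN (reading of SAP 7.8.2). ALT/AST may enter at up to 1.5xULN (Protocol 4.4). A liver-test DLT needs more than 3xULN (SAP 4.3). Stage 1 has 10 patients and up to 8 single doses, with chemistry drawn 24 hours after each dose (Protocol 3.1, Period 2.1).

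**1. High at baseline.** The largest rise that shows neither a shift nor a DLT is 3.0 divided by the baseline multiple.

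| Baseline (xULN) | Ceiling | Fold rise |
|---|---|---|
| 1.5 | 3.0 / 1.5 | 2.0 |
| just above 1.0 | 3.0 / 1.0 | just under 3.0 |
| 2.0 (sensitivity only) | 3.0 / 2.0 | 1.5 |

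The 2.0xULN row applies to ALT/AST only if a later pre-dose draw exceeds the screening cap. The visit schedules show one pre-dose chemistry, at run-in Day 1. A later value would come from an unscheduled draw or from the end-of-period testing in Protocol 9.5.

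**2. Normal at baseline.** The shift to High is visible but its size is not. The Normal-to-High cell without a DLT covers rises from above 1.0/baseline up to 3.0/baseline:

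- baseline 1.0xULN: above 1.0-fold to 3.0-fold;
- baseline 0.5xULN: above 1.0 / 0.5 = 2.0-fold to 3.0 / 0.5 = 6.0-fold.

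**3. Repeats.** Suppose a scheduled value of 3.0xULN is followed by an unscheduled 1.0xULN. Under SAP 8.5 the table shows Normal for that visit, and the peak is only in the listing. If the first value was flagged SG, it is also recorded as an adverse laboratory event.

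**4. Whether another table fills the gap.**

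- SAP 7.1 defines statistics for continuous variables in general, but 7.8.2 specifically assigns frequency distributions to all laboratory results.
- SAP 7.8.1 tabulates TEAEs by maximum CTCAE grade, but a laboratory value gets there only if judged clinically significant (Protocol 9.11 and 10.3.1).
- SAP 7.8.6 tabulates DLTs, which for liver tests start above 3xULN.
- By contrast, SAP 7.8.3 plans change from baseline for temperature, respiration rate, heart rate and weight.

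**5. Volume.** Stage 1 can produce at most 10 x 8 = 80 post-dose panels, or 80 x 3 = 240 ALT, AST and total bilirubin results. This is the amount a reader would have to rescale from listings. It is not a count of affected results.

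**6. Density of a replacement.** Five bands by 8 doses by 3 analytes is 120 cells, on average at most 240 / 120 = 2.0 results each. A five-by-five shift at every dose would be 5 x 5 x 3 x 8 = 600 cells, at most 240 / 600 = 0.4 each, spread over 24 grids (8 doses x 3 analytes). One shift table per stage is 25 cells per analyte. It is also sparse in Stage 1 (10 / 25 = 0.4 patients per cell), but there are only three grids to read.

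**The case against.** The best opposing case is that nothing that matters operationally depends on these tables. In Stage 1, chemistry is reviewed the evening before the next dose, and a value above 3xULN stops the patient. A physician reviews out-of-range values within 24 hours of receipt. Significant ones become adverse events and are tabulated by grade. Every original and repeat value is listed, and with 10 and 40 patients a listing can be read. SAP 1 allows supplementary analyses. The hepatic toxicity was seen with intravenous dosing, at plasma levels of 5-10 µg/ml, whereas Protocol 1.3 predicts an oral peak of about 2 ng/ml at 200 mg.

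Most of this stands, and it limits the consequence. It does not remove the gap for rises that no one judged significant. The low oral exposure is a prediction from animal bioavailability, and the amended Stage 2 range reaches 250 mg (SAP 2.1), above the 200 mg to which that prediction refers.

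A reader might infer several stronger things that the documents do not support:

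- **That liver injury could go unmonitored, or that DLTs are undercounted.** The stopping and DLT rules do not use these tables.
- **That data are lost.** The listings hold every value.
- **That SAP 8.5 routinely hides important peaks.** Retesting is mandatory only for SG values, and those are recorded as adverse laboratory events. What can drop out of tabulated output altogether is a non-SG peak that happened to be redrawn.
- **That the 1.5xULN entry cap applies to bilirubin.** It covers ALT and AST only. No numeric bilirubin limit is given, so the fold ceilings from the permitted baseline range are document-based for the enzymes alone.
- **That the fold ratios are effect sizes.** They are ratios of category boundaries and say nothing about frequency.

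**Conclusion.** The point holds as a reporting weakness. As written, no laboratory table shows the size of an ALT, AST or bilirubin rise between 1 and 3xULN. A 2.0-fold enzyme rise from 1.5xULN, or one just under 3.0-fold from just above 1.0xULN, appears as High-to-High with no liver-test DLT. A peak that is later repeated can leave the table.

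This rests on reading High as above the reporting laboratory's ULN, and on SAP 7.8.2 taking precedence over the general wording of 7.1. The share of patients in each baseline band is not given, so the number affected is unknown and could be zero.

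No decision or DLT count changes. The gain is a clearer hepatic safety summary, mainly in Stage 1. It is small in Stage 2, because the amended schedule has one on-drug chemistry visit (Visit 3, SAP Table 4). The change is worth making before database lock because it is cheap; it is not a reason to doubt the trial's conduct.

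**What to change.** Add to SAP 7.8.2:

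- Express ALT, AST and total bilirubin as multiples of the reporting laboratory's ULN.
- Take the worst post-baseline multiple, including unscheduled and repeat results, and state that SAP 8.5 does not apply to these tables.
- Tabulate it as <=1, >1-1.5, >1.5-2, >2-3 and >3xULN. Give frequency counts by dose level in Stage 1 and by period in Stage 2.
- Add one baseline-to-worst shift table per stage, not per dose.
- Define baseline for these tables as the last result before the first dose in that stage. SAP 8.1 refers only to first dosing in Stage 1, and the Stage 2 patients are different people (Protocol 10.1.2).
- Keep low/normal/high for the other analytes.

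The cost is one derived variable and a few small, sparse tables, with no new sampling. The documents do not say whether numeric ULNs are in the database. The >3xULN DLT analysis needs them in any case; if only flags are stored, they must be taken from the local laboratory reports. The 2xULN cut is a reviewer's choice that appears nowhere in the documents, and the >2-3 band still merges a range of values, so the listing remains the reference for individual patients.

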7.8.3 Vital Signs

Stage 1 and up to end of fixed dosing period in Stage 2

Vital signs (Stage 1 and up to end of fixed dosing period in Stage 2) for body temperature, respiration rate, heart rate and weight will be summarized by period, together with the change from baseline. Baseline for body temperature, respiration rate, heart rate and weight will be the last assessment during the run-in period.

Systolic and diastolic blood pressure will be summarized by time point (pre-dose and 2 hours post-dose) and dose period separately for each position (lying down and sitting). Baseline for predose in each dose period and washout will be the last assessment during the run-in period. Baseline for 2 hour post dose in each dose period will be the assessment at predose at that dose period.

All summaries will be provided for the safety population.

Randomization period in Stage 2

Additionally, the above summaries will be provided for viral signs during the randomization period by treatment for randomized population.

7.8.4 Electrocardiogram (ECG)

Stage 1 and up to end of fixed dosing period in Stage 2

ECG findings will be classified as normal vs abnormal. The number and percentage of each category will be summarized using frequency table for run-in, dose period, and wash-out. The denominators for calculating the percentages will be based on the number of subjects with non-missing values in each period for the Safety Population. Baseline will be defined as the most recent measurement taken in the run-in period.

Randomization period in Stage 2

Additionally, the above summaries will be provided for ECG during the randomization period by treatment for randomized population.

Detailed ECG results will be provided in a data listing.

7.8.5 Physical Examination

Stage 1 and up to end of fixed dosing period in Stage 2

Summary of physical examinations will present frequency distribution by body system and each period. The denominators for calculating the percentages will be based on the number of subjects evaluated for a particular body system of each dose level in the Safety Population.

Randomization period in Stage 2

Additionally, the above summaries will be provided by treatment for randomized population.

Details on physical examinations will be provided in a data listing.

7.8.6 Analysis of Tolerability Data

Stage 1 and up to end of fixed dosing period in Stage 2

Tolerability will be measured by DLT endpoints defined in Section 4.3.

The frequency of each tolerability endpoints including recurrent vomiting, recurrent diarrhea, abdominal pain and postural hypertension, and etc. will be summarized by dose (Stage 1) or for treatment period (Stage 2). Percentages will be based on the number of subjects in each dose level (Stage 1) or the number of subjects (Stage 2) in the safety population.

Randomization period in Stage 2

Additionally, the above summaries will be provided during the randomization period by treatment for randomized population.

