9.2 Observations and Measurements

All the questionnaires will be filled in according to the schedule. In Trail-Making B, the Trail will be completed twice, and both results will be reported. If the patient fails to complete the Trail, it will be reported as failed to complete.

Stool diaries and sleep diaries: Patients will be instructed how to fill the diaries daily throughout the study. They will be told to mark use of suppositories or enemas.

Vital signs: Per study procedures listings and for PK subjects Randomization Day 1 and Day 6 before dose and 2 hours after dose.

An I-Button which measures skin temperature and attached to a wrist band will be worn for 5 consecutive 24 hr periods from day 8-13 during Period 1, throughout the dosing period and randomized period and for the first five days of the wash-out period, and will not be removed except for brief periods during a bath/shower. Patients will be shown how to wear the I-Buttons with the button facing the skin and overlying the radial artery.

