6.2 Safety Population

For each stage, safety Population will consist of all subjects who receive at least one dose of ENT-01 during that stage.

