7.1 General Statistical Procedures

Frequency distributions for categorical variables will be provided as counts of subjects and percentages. Percentages will be based on the number of subjects with a non-missing parameter unless missing category is presented. Percentages will be reported to one decimal place.

The descriptive statistics for continuous variables will be number of subjects, arithmetic mean, standard deviation (SD), median, quartiles (Q1, Q3), minimum and maximum. Arithmetic mean, median, Q1, and Q3 will be reported to 1 more decimal place than the raw data, while the SD will be reported to two more decimal places than the raw data.

In addition to the above descriptive statistics, the coefficient of variation (CV%) will also be used for the summaries of drug concentration data and pharmacokinetic parameter values. The geometric means will be calculated for AUC and Cmax values.

All data listings that contain an evaluation date will also contain a relative study day.

Missing values will not be imputed.

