8.2 Analysis Visit Window

For safety parameters excluding clinical laboratory data, measurements collected from unscheduled visits will not be included in the by-visit summary tables but will be included in the listings. Early termination visits for safety measurements will not be mapped to any scheduled post-baseline visit, but will be used as the last assessment during treatment period.

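### In Stage 2, SAP 7.8.3 plans pre-dose/2-hour blood-pressure pairs that are not scheduled up to the end of fixed dosing, and SAP 7.8.6 counts dosed patients with no on-treatment LFT, weight or BP value as free of those DLTs

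*SAP*

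**What the plan says.** **DLT percentages.** SAP 7.8.6, for Stage 2 up to the end of fixed dosing, divides by "the number of subjects (Stage 2) in the safety population". SAP 6.2 defines that population as "all subjects who receive at least one dose of ENT-01 during that stage", so no post-dose measurement is needed to be in it. SAP 4.3 lists the DLTs. Two rest wholly on a measurement: LFTs above three times the upper limit of normal, and weight loss of 10% or more. Postural hypotension can be met by symptoms or by a systolic reading below 80 or a diastolic reading below 40 mmHg. The others are symptoms. The general rule in SAP 7.1 reads: "Percentages will be based on the number of subjects with a non-missing parameter unless missing category is presented". SAP 7.8.2 applies the same principle to laboratory tests.

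**Blood pressure.** Under a heading that covers Stage 1 and Stage 2 to the end of fixed dosing, SAP 7.8.3 has BP "summarized by time point (pre-dose and 2 hours post-dose) and dose period separately for each position (lying down and sitting". It adds: "Baseline for 2 hour post dose in each dose period will be the assessment at predose at that dose period".

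**Early leavers and unscheduled values.** Protocol 4.5 asks for a discontinuation visit with all assessments, if possible. Under SAP 8.2, early-termination safety values are not mapped to a scheduled visit but "will be used as the last assessment during treatment period". SAP 8.5 states: "For laboratories results at unscheduled visits, it will be treated as repeated laboratory results for the closest previous visit".

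**The concern.** Safety and tolerability are a primary objective of Stage 2 (SAP 3.2.1). A DLT that depends on a laboratory value, a weight or a BP reading can be ruled out only in someone who was measured. Patients who stop during escalation are the ones most likely to have no such value, and SAP 7.8.6 keeps them in the denominator as if they had been checked. A reported 0 of 40 would not show in that table how many patients were never assessed.

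The BP rule has a different fault. It carries the Stage 1 measurement pattern over to a part of Stage 2 where readings are not taken that way. SAP 7.8.3 summarizes temperature, respiration, heart rate and weight by period but gives BP only the timed layout. The Visit 3 BP, the one on-treatment session in Table 4, is therefore left without a usable summary rule.

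**Working it through.** **Step 1. When the measurements are scheduled in Stage 2.**

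| | SAP Table 3 (July 2017) | SAP Table 4 (February 2018) |
|---|---|---|
| Chemistry before first dose | Visit 1 | Visit 1 |
| Weight and BP before first dose | Visits 1 and 2 | Visits 1 and 2 |
| Period 3.2 columns | phone calls only | phone calls only |
| First chemistry, weight and BP after first dose | Visit 3 (day before randomization; randomization Day 1 for PK patients) | Visit 3 (fixed-dose Day 4) |
| BP positions | lying, then sitting or standing | supine, then standing |

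Both tables give no scheduled on-treatment value before Visit 3. Protocol 9.5 complicates this for chemistry, because it asks for laboratory tests at baseline and at the end of each Period. In the July 2017 design, Period 3.2 includes fixed dosing, so Visit 3 meets that requirement. In Table 4, escalation is a Period of its own and no chemistry is shown at its end.

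**Step 2. Count the pre-dose/2-hour BP pairs.**

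| Window | Source | Scheduled pairs |
|---|---|---|
| Stage 1 dosing | SAP Table 2, footnote 1 | yes |
| Stage 2, first dose to end of fixed dosing, July 2017 | Table 3 | 0 |
| Same window, February 2018 | Table 4 | 0 |
| Randomized period, July 2017, PK patients | Protocol 9.2 | 2 days x 10 planned patients = 20 |
| Randomized period, February 2018 | SAP 2.1 (period removed) | 0 |

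The fourth row rests on Protocol 9.2, which takes vital signs "for PK subjects Randomization Day 1 and Day 6 before dose and 2 hours after dose". The 10 patients are the 7 on ENT-01 and 3 on placebo in SAP 6.1.2. The documents do not say how many were sampled before randomization was dropped. For PK patients the Visit 3 pre-dose reading may serve as an end-of-fixed-dose value, but its 2-hour partner follows the first randomized dose, so no pair falls inside the fixed-dose window.

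**Step 3. Size of the denominator effect.** The plan's own size first: 34 evaluable patients at 15% drop-out gives 34 / (1 - 0.15) = 40, so 40 - 34 = 6 planned drop-outs (SAP 2.2).

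Let N be the patients dosed, m those with no on-treatment value, and x those with the DLT. The SAP reports x/N; the rate among assessed patients is x/(N - m). Their ratio is (N - m)/N, so the reported rate is low by m/N in relative terms. The documents do not give m, so I assume 0 to 6 of 40:

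- m = 0: 0/40 = 0%.
- m = 6: 6/40 = 15%.

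| Events | Out of 40 | Out of 34 |
|---|---|---|
| 1 | 2.5% | 2.9% |
| 2 | 5.0% | 5.9% |
| 3 | 7.5% | 8.8% |

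At m = 4, one event is 1/36 = 2.8%. With no events, the exact one-sided 95% upper bound is 1 - 0.05^(1/40) = 7.2% with 40 assessed and 1 - 0.05^(1/34) = 8.4% with 34.

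**The case against.** A section-specific rule may depart from the general one, and counting events over everyone treated is how SAP 7.8.1 handles adverse events. That suits the symptom-based DLTs, which daily calls can pick up in any dosed patient. It suits LFT and weight DLTs less well, because absence of a value is not absence of the event, and SAP 7.8.2 already uses non-missing denominators for the same laboratory data.

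The gap is also narrower than the schedules alone suggest. Discontinuation visits and SAP 8.2 supply on-treatment values for early leavers who attend, nothing bars unscheduled tests, and the other safety tables, disposition counts and listings show who was measured. This stands. It limits the size of the problem, but the visit is required only if possible and the DLT table itself would not show the missing patients. The upper end, m = 6, needs all six drop-outs to be dosed, to leave before Visit 3 and to miss the discontinuation visit; run-in drop-outs are not in the safety population.

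Several stronger readings are tempting and are not supported:

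- *Stage 2 has no pre-dose/2-hour readings.* PK patients have them on two randomized days under the July 2017 protocol, and SAP 7.8.3 plans a randomization-period summary.
- *These parameters go unmeasured before Visit 3.* Run-in values exist; the gap starts at the first dose.
- *SAP 8.5 files an escalation chemistry under the run-in.* That depends on what counts as a visit. A Table 4 footnote refers to a phone call as a visit, and nothing says SAP 8.5 governs how DLTs are derived.
- *The period headings are too short for the wider dose range, or an extra safety visit is needed.* Both rest on the February 2018 amendment, which is not among the documents. Table 1 also still shows the July 2017 design, so setting it against the amended range mixes versions.

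**Conclusion.** The point holds in two limited parts, and it is minor.

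The BP table in SAP 7.8.3 cannot be produced for Stage 2 up to the end of fixed dosing: neither schedule has any pre-dose/2-hour pair in that window, and Table 4's positions (supine and standing) differ from those the SAP names. This needs no numerical assumption; it rests on Tables 3 and 4 as printed.

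The SAP 7.8.6 denominator treats an unmeasured patient as free of the LFT, weight and numeric-BP DLTs. The understatement is 0% to 15% in relative terms for an assumed 0 to 6 of 40 unmeasured, which is about 0.4 percentage points for one event at the upper end (2.9% - 2.5%). If every early leaver attends a discontinuation visit, it is zero. These percentages are descriptive; no test or threshold is attached to them. For chemistry, the gap before Visit 3 is read from the schedules and sits uneasily with Protocol 9.5.

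**What to change.** **SAP 7.8.3.** Limit the pre-dose/2-hour BP table by dose period to Stage 1, and keep the timed readings of PK patients in the randomization-period summary. For Stage 2, summarize Visit 3 and wash-out BP by the position actually measured (supine and standing under Table 4) as change from the last run-in value.

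**SAP 7.8.6.** For the LFT and weight DLTs, use safety-population patients with at least one on-treatment value of that parameter, counting early-termination and unscheduled values, and report how many were not assessed. Keep the whole safety population for symptom-based DLTs, including postural hypotension, which has both a symptom and a numeric route, and report how many patients have no on-treatment BP.

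**SAP 8.5, secondary.** State that a chemistry drawn after the first dose is never treated as a repeat of a run-in visit.

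A note should also record that Protocol 9.5 calls for end-of-Period chemistry that Table 4 does not show for escalation.

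Cost: edits to SAP text and to the table specifications that follow from it. No new data, visits or patients.
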